	≥ 65 years	xxx	xxx(xx.xx)	[xx.xx, xx.xx]	x.xxxx
	< 65 years	xxx	xxx(xx.xx)	[xx.xx, xx.xx]	
Classification	Total	xxx	xxx(xx.xx)	-	
	Outpatient	xxx	xxx(xx.xx)	[xx.xx, xx.xx]	x.xxxx
	Inpatient	xxx	xxx(xx.xx)	[xx.xx, xx.xx]	
	Total	xxx	xxx(xx.xx)	-	

¹⁾Chi-square Test

²⁾Fisher's Exact Test

*Statistically significant

Programming note: This table is repeated for each sub-group with the following table title and footnote.

Title : [Table 23-x] Occurrence status of adverse events by demographic characteristics (sub-group x: N=xxx)

Footnote: Sub-group 1: Subjects who are first administered INLYTA® during the study period

Sub-group 2: Subjects who has continued administration of INLYTA® since the time prior to the contract date

[Table 24] Occurrence status of adverse events by other baseline characteristics

Factor	Classification	No. of Subjects	Incidence of AE n(%)	[95% CI]	p-value ¹⁾²⁾
Duration of aRCC	Category 1	xxx	xxx(xx.xx)	[xx.xx, xx.xx]	x.xxxx
	Category 2	xxx	xxx(xx.xx)	[xx.xx, xx.xx]	
	Category 3	xxx	xxx(xx.xx)	[xx.xx, xx.xx]	
	...	xxx	xxx(xx.xx)	[xx.xx, xx.xx]	
	Total	xxx	xxx(xx.xx)	-	
Cell component of aRCC	Clear cell	xxx	xxx(xx.xx)	[xx.xx, xx.xx]	x.xxxx
	Other	xxx	xxx(xx.xx)	[xx.xx, xx.xx]	
	Total	xxx	xxx(xx.xx)	-	
Metastasis	Yes [§]	xxx	xxx(xx.xx)	[xx.xx, xx.xx]	x.xxxx
	Liver	xxx	xxx(xx.xx)	[xx.xx, xx.xx]	
	Lung	xxx	xxx(xx.xx)	[xx.xx, xx.xx]	
	Bone	xxx	xxx(xx.xx)	[xx.xx, xx.xx]	
	Brain	xxx	xxx(xx.xx)	[xx.xx, xx.xx]	
	Skin	xxx	xxx(xx.xx)	[xx.xx, xx.xx]	
	Lymph nodes	xxx	xxx(xx.xx)	[xx.xx, xx.xx]	
	Other	xxx	xxx(xx.xx)	[xx.xx, xx.xx]	
	No	xxx	xxx(xx.xx)	[xx.xx, xx.xx]	
	Total	xxx	xxx(xx.xx)	-	
Primary lesion surgery	Done	xxx	xxx(xx.xx)	[xx.xx, xx.xx]	x.xxxx
	Not done	xxx	xxx(xx.xx)	[xx.xx, xx.xx]	
	Total	xxx	xxx(xx.xx)	-	

Dummy Table

Factor	Classification	No. of Subjects	Incidence of AE n(%)	[95% CI]	p-value ¹⁾²⁾
	Total	xxx	xxx(xx.xx)	-	
Medical history	Yes	xxx	xxx(xx.xx)	[xx.xx, xx.xx]	x.xxxx
	No	xxx	xxx(xx.xx)	[xx.xx, xx.xx]	
	Total	xxx	xxx(xx.xx)	-	
Renal impairment	Yes	xxx	xxx(xx.xx)	[xx.xx, xx.xx]	x.xxxx
	No	xxx	xxx(xx.xx)	[xx.xx, xx.xx]	
	Total	xxx	xxx(xx.xx)	-	
Hepatic impairment	Yes	xxx	xxx(xx.xx)	[xx.xx, xx.xx]	x.xxxx
	No	xxx	xxx(xx.xx)	[xx.xx, xx.xx]	
	Total	xxx	xxx(xx.xx)	-	
Allergic history	Yes	xxx	xxx(xx.xx)	[xx.xx, xx.xx]	x.xxxx
	No	xxx	xxx(xx.xx)	[xx.xx, xx.xx]	
	Total	xxx	xxx(xx.xx)	-	
Prior chemotherapy	Yes	xxx	xxx(xx.xx)	[xx.xx, xx.xx]	x.xxxx
	No	xxx	xxx(xx.xx)	[xx.xx, xx.xx]	
	Unknown	xxx	xxx(xx.xx)	[xx.xx, xx.xx]	
	Total	xxx	xxx(xx.xx)	-	
Prior immunotherapy	Yes	xxx	xxx(xx.xx)	[xx.xx, xx.xx]	x.xxxx
	No	xxx	xxx(xx.xx)	[xx.xx, xx.xx]	
	Unknown	xxx	xxx(xx.xx)	[xx.xx, xx.xx]	
	Total	xxx	xxx(xx.xx)	-	
Prior radiation therapy	Yes	xxx	xxx(xx.xx)	[xx.xx, xx.xx]	x.xxxx
	No	xxx	xxx(xx.xx)	[xx.xx, xx.xx]	
	Unknown	xxx	xxx(xx.xx)	[xx.xx, xx.xx]	
	Total	xxx	xxx(xx.xx)	-	
Concomitant medication	Yes	xxx	xxx(xx.xx)	[xx.xx, xx.xx]	x.xxxx
	No	xxx	xxx(xx.xx)	[xx.xx, xx.xx]	
	Total	xxx	xxx(xx.xx)	-	
Duration of administration	Category 1	xxx	xxx(xx.xx)	[xx.xx, xx.xx]	x.xxxx
	Category 2	xxx	xxx(xx.xx)	[xx.xx, xx.xx]	
	Category 3	xxx	xxx(xx.xx)	[xx.xx, xx.xx]	
	...	xxx	xxx(xx.xx)	[xx.xx, xx.xx]	
	Total	xxx	xxx(xx.xx)	-	
Daily average dose	Category 1	xxx	xxx(xx.xx)	[xx.xx, xx.xx]	x.xxxx
	Category 2	xxx	xxx(xx.xx)	[xx.xx, xx.xx]	
	Category 3	xxx	xxx(xx.xx)	[xx.xx, xx.xx]	
	...	xxx	xxx(xx.xx)	[xx.xx, xx.xx]	
	Total	xxx	xxx(xx.xx)	-	

¹⁾Overlapped

²⁾Chi-square Test

²⁾Fisher's Exact Test

*Statistically significant

Programming note: This table is repeated for each sub-group with the following table title and footnote.

Title : [Table 24-x] Occurrence status of adverse events by other baseline characteristics (sub-group x: N=xxx)

Footnote: Sub-group 1: Subjects who are first administered INLYTA® during the study period

Sub-group 2: Subjects who has continued administration of INLYTA® since the time prior to the contract date

Dummy Table

[Table 25] Multivariate logistic regression for occurrence status of adverse events

Factor	Classification	Estimate	Standard Error	p-value	Odds Ratio	[95% CI]
Intercept		xx.xx	xx.xx	x.XXXX		
Factor 1	Yes	xx.xx	xx.xx	x.XXXX	xx.xx	[xx.xx, xx.xx]
	No	Reference				
Factor 2	Category 1	Reference				
	Category 2	xx.xx	xx.xx	x.XXXX	xx.xx	[xx.xx, xx.xx]
...						
...						

Response variable: occurrence status of adverse events

*Statistically significant

Programming note1: This analysis will be performed in the re-examination report only.

Programming note2: This table is repeated for each sub-group with the following table title and footnote.

Title : [Table 25-x] Multivariate logistic regression for occurrence status of adverse events (sub-group x: N=xxx)

Footnote: Sub-group 1: Subjects who are first administered INLYTA® during the study period

Sub-group 2: Subjects who has continued administration of INLYTA® since the time prior to the contract date

[Table 26] Best overall response and objective response rate

Factor	Classification	Sub-group 1	Sub-group 2	Total
		(N=xxx) n(%)	(N=xxx) n(%)	(N=xxx) n(%)
Best overall response	Objective response rate (ORR)†	xxx(xx.xx)	xxx(xx.xx)	xxx(xx.xx)
	Complete response (CR)	xxx(xx.xx)	xxx(xx.xx)	xxx(xx.xx)
	Partial response (PR)	xxx(xx.xx)	xxx(xx.xx)	xxx(xx.xx)
	Stable disease (SD)	xxx(xx.xx)	xxx(xx.xx)	xxx(xx.xx)
	Progressive disease (PD)	xxx(xx.xx)	xxx(xx.xx)	xxx(xx.xx)
	Not evaluable (NE)	xxx(xx.xx)	xxx(xx.xx)	xxx(xx.xx)
	Not done (ND)	xxx(xx.xx)	xxx(xx.xx)	xxx(xx.xx)
	Total	xxx(xx.xx)	xxx(xx.xx)	xxx(xx.xx)

Sub-group 1: Subjects who are first administered INLYTA® during the study period

Sub-group 2: Subjects who has continued administration of INLYTA® since the time prior to the contract date

†ORR: The numerator is: number of subjects who achieves a best overall response of CR or PR

The denominator is: number of subjects in the efficacy analysis set

Dummy Table

[Table 27] Summary statistics for progression-free survival

Factor	Classification	Number of subjects n(%)
Event rate	Event	xxx(xx.xx)
	Progressive disease	xxx(xx.xx)
	Death	xxx(xx.xx)
Censored rate	Censored	xxx(xx.xx)
PFS time (day)	75th percentile [95% CI]	xx.xx[xx.xx, xx.xx)
	50th percentile [95% CI]	xx.xx[xx.xx, xx.xx)
	25th percentile [95% CI]	xx.xx[xx.xx, xx.xx)

[figure not shown]
Programming note: This table is repeated for each sub-group with the following table title and footnote.

Title : [Table 27-x] Summary statistics for progression-free survival (sub-group x: N=xxx)

Footnote: Sub-group 1: Subjects who are first administered INLYTA® during the study period

Sub-group 2: Subjects who has continued administration of INLYTA® since the time prior to the contract date

[Figure 1] Kaplan-Meier curve for progression-free survival

Programming note: This table is repeated for each sub-group with the following table title and footnote.

Title : [Figure 1-x] Kaplan-Meier curve for progression-free survival (sub-group x: N=xxx)

Footnote: Sub-group 1: Subjects who are first administered INLYTA® during the study period

Sub-group 2: Subjects who has continued administration of INLYTA® since the time prior to the contract date

Dummy Table

[Table 28] Summary statistics for time to progression

Factor	Classification	Number of subjects n(%)
Event rate	Progressive disease	xxx(xx.xx)
Censored rate	Censored	xxx(xx.xx)
TTP time (day)	75th percentile [95% CI)	xx.xx[xx.xx, xx.xx)
	50th percentile [95% CI)	xx.xx[xx.xx, xx.xx)
	25th percentile [95% CI)	xx.xx[xx.xx, xx.xx)

[figure not shown]
Programming note: This table is repeated for each sub-group with the following table title and footnote.

Title : [Table 28-x] Summary statistics for time to progression (sub-group x: N=xxx)

Footnote: Sub-group 1: Subjects who are first administered INLYTA® during the study period

Sub-group 2: Subjects who has continued administration of INLYTA® since the time prior to the contract date

[Figure 2] Kaplan-Meier curve for time to progression

Programming note: This table is repeated for each sub-group with the following table title and footnote.

Title : [Figure 2-x] Kaplan-Meier curve for time to progression (sub-group x: N=xxx)

Footnote: Sub-group 1: Subjects who are first administered INLYTA® during the study period

Sub-group 2: Subjects who has continued administration of INLYTA® since the time prior to the contract date

Dummy Table

[Table 29] Objective response rate by demographic characteristics

Factor	Classification	No. of Subjects	Objective Response Rate n(%)	[95% CI]	p-value ¹⁾²⁾
Sex	Male	xxx	xxx(xx.xx)	[xx.xx, xx.xx]	x.xxxx
	Female	xxx	xxx(xx.xx)	[xx.xx, xx.xx]	
	Total	xxx	xxx(xx.xx)	-	
Age	Category 1	xxx	xxx(xx.xx)	[xx.xx, xx.xx]	x.xxxx
	Category 2	xxx	xxx(xx.xx)	[xx.xx, xx.xx]	
	Category 3	xxx	xxx(xx.xx)	[xx.xx, xx.xx]	
	...	xxx	xxx(xx.xx)	[xx.xx, xx.xx]	
	Total	xxx	xxx(xx.xx)	-	
Pediatric	< 19 years	xxx	xxx(xx.xx)	[xx.xx, xx.xx]	x.xxxx
	≥ 19 years	xxx	xxx(xx.xx)	[xx.xx, xx.xx]	
	Total	xxx	xxx(xx.xx)	-	
Geriatric	≥ 65 years	xxx	xxx(xx.xx)	[xx.xx, xx.xx]	x.xxxx
	< 65 years	xxx	xxx(xx.xx)	[xx.xx, xx.xx]	
	Total	xxx	xxx(xx.xx)	-	
Classification	Outpatient	xxx	xxx(xx.xx)	[xx.xx, xx.xx]	x.xxxx
	Inpatient	xxx	xxx(xx.xx)	[xx.xx, xx.xx]	
	Total	xxx	xxx(xx.xx)	-	

¹⁾Chi-square Test

²⁾Fisher's Exact Test

*Statistically significant

Programming note: This table is repeated for each sub-group with the following table title and footnote.

Title : [Table 29-x] Objective response rate by demographic characteristics (sub-group x: N=xxx)

Footnote: Sub-group 1: Subjects who are first administered INLYTA® during the study period

Sub-group 2: Subjects who has continued administration of INLYTA® since the time prior to the contract date

[Table 30] Objective response rate by demographic and other baseline characteristics

Factor	Classification	No. of Subjects	Objective Response Rate n(%)	[95% CI]	p-value ¹⁾²⁾
Duration of aRCC	Category 1	xxx	xxx(xx.xx)	[xx.xx	x.xxxx
	Category 2	xxx	xxx(xx.xx)	[xx.xx, xx.xx]	
	Category 3	xxx	xxx(xx.xx)	[xx.xx, xx.xx]	
	...	xxx	xxx(xx.xx)	[xx.xx, xx.xx]	
	Total	xxx	xxx(xx.xx)	-	
Cell component of aRCC	Clear cell	xxx	xxx(xx.xx)	[xx.xx, xx.xx]	x.xxxx
	Other	xxx	xxx(xx.xx)	[xx.xx, xx.xx]	
	Total	xxx	xxx(xx.xx)	-	
Metastasis	Yes [§]	xxx	xxx(xx.xx)	[xx.xx, xx.xx]	x.xxxx
	Liver	xxx	xxx(xx.xx)	[xx.xx, xx.xx]	
	Lung	xxx	xxx(xx.xx)	[xx.xx, xx.xx]	
	Bone	xxx	xxx(xx.xx)	[xx.xx, xx.xx]	
	Brain	xxx	xxx(xx.xx)	[xx.xx, xx.xx]	
	Skin	xxx	xxx(xx.xx)	[xx.xx, xx.xx]	
	Lymph	xxx	xxx(xx.xx)	[xx.xx, xx.xx]	
	nodes				
	Other	xxx	xxx(xx.xx)	[xx.xx, xx.xx]	
	No	xxx	xxx(xx.xx)	[xx.xx, xx.xx]	

Dummy Table

Factor	Classification	No. of Subjects	Objective Response Rate n(%)	[95% CI]	p-value ¹⁾²⁾
	Total	xxx	xxx(xx.xx)	-	
Primary lesion surgery	Done	xxx	xxx(xx.xx)	[xx.xx, xx.xx]	x.xxxx
	Not done	xxx	xxx(xx.xx)	[xx.xx, xx.xx]	
	Total	xxx	xxx(xx.xx)	-	
Medical history	Yes	xxx	xxx(xx.xx)	[xx.xx, xx.xx]	x.xxxx
	No	xxx	xxx(xx.xx)	[xx.xx, xx.xx]	
	Total	xxx	xxx(xx.xx)	-	
Renal impairment	Yes	xxx	xxx(xx.xx)	[xx.xx, xx.xx]	x.xxxx
	No	xxx	xxx(xx.xx)	[xx.xx, xx.xx]	
	Total	xxx	xxx(xx.xx)	-	
Hepatic impairment	Yes	xxx	xxx(xx.xx)	[xx.xx, xx.xx]	x.xxxx
	No	xxx	xxx(xx.xx)	[xx.xx, xx.xx]	
	Total	xxx	xxx(xx.xx)	-	
Allergic history	Yes	xxx	xxx(xx.xx)	[xx.xx, xx.xx]	x.xxxx
	No	xxx	xxx(xx.xx)	[xx.xx, xx.xx]	
	Total	xxx	xxx(xx.xx)	-	
Prior chemotherapy	Yes	xxx	xxx(xx.xx)	[xx.xx, xx.xx]	x.xxxx
	No	xxx	xxx(xx.xx)	[xx.xx, xx.xx]	
	Unknown	xxx	xxx(xx.xx)	[xx.xx, xx.xx]	
	Total	xxx	xxx(xx.xx)	-	
Prior immunotherapy	Yes	xxx	xxx(xx.xx)	[xx.xx, xx.xx]	x.xxxx
	No	xxx	xxx(xx.xx)	[xx.xx, xx.xx]	
	Unknown	xxx	xxx(xx.xx)	[xx.xx, xx.xx]	
	Total	xxx	xxx(xx.xx)	-	
Prior radiation therapy	Yes	xxx	xxx(xx.xx)	[xx.xx, xx.xx]	x.xxxx
	No	xxx	xxx(xx.xx)	[xx.xx, xx.xx]	
	Unknown	xxx	xxx(xx.xx)	[xx.xx, xx.xx]	
	Total	xxx	xxx(xx.xx)	-	
Concomitant medication	Yes	xxx	xxx(xx.xx)	[xx.xx, xx.xx]	x.xxxx
	No	xxx	xxx(xx.xx)	[xx.xx, xx.xx]	
	Total	xxx	xxx(xx.xx)	-	
Duration of administration	Category 1	xxx	xxx(xx.xx)	[xx.xx, xx.xx]	x.xxxx
	Category 2	xxx	xxx(xx.xx)	[xx.xx, xx.xx]	
	Category 3	xxx	xxx(xx.xx)	[xx.xx, xx.xx]	
	...	xxx	xxx(xx.xx)	[xx.xx, xx.xx]	
	Total	xxx	xxx(xx.xx)	-	
Daily average dose	Category 1	xxx	xxx(xx.xx)	[xx.xx, xx.xx]	x.xxxx
	Category 2	xxx	xxx(xx.xx)	[xx.xx, xx.xx]	
	Category 3	xxx	xxx(xx.xx)	[xx.xx, xx.xx]	
	...	xxx	xxx(xx.xx)	[xx.xx, xx.xx]	
	Total	xxx	xxx(xx.xx)	-	

[§]Overlapped

¹⁾Chi-square Test

²⁾Fisher's Exact Test

*Statistically significant

Programming note: This table is repeated for each sub-group with the following table title and footnote.

Title : [Table 30-x] Objective response rate by other baseline characteristics (sub-group x: N=xxx)

Footnote: Sub-group 1: Subjects who are first administered INLYTA® during the study period

Sub-group 2: Subjects who has continued administration of INLYTA® since the time prior to the contract date

Dummy Table

[Table 31] Multivariate logistic regression for objective response rate

Factor	Classification	Estimate	Standard Error	p-value	Odds Ratio	[95% CI]
Intercept		xx.xx	xx.xx	x.XXXX		
Factor 1	Yes	xx.xx	xx.xx	x.XXXX	xx.xx	[xx.xx, xx.xx]
	No	Reference				
Factor 2	Category 1	Reference				
	Category 2	xx.xx	xx.xx	x.XXXX	xx.xx	[xx.xx, xx.xx]
...	...					
...	...					

Response variable: objective response

*Statistically significant

Programming note1: This analysis will be performed in the re-examination report only.

Programming note2: This table is repeated for each sub-group with the following table title and footnote.

Title : [Table 31-x] Multivariate logistic regression for objective response rate (sub-group x: N=xxx)

Footnote: Sub-group 1: Subjects who are first administered INLYTA® during the study period

Sub-group 2: Subjects who has continued administration of INLYTA® since the time prior to the contract date

Dummy Table

[Table 32] Adverse events and adverse drug reactions of pediatric subjects (aged < 19) (N=xxx)

System Organ Class [§] Preferred Term	Adverse events	Adverse drug reactions
	n(%), [E]	n(%), [E]
System Organ Class	xxx(xx.xx), [xxx]	xxx(xx.xx), [xxx]
Preferred Term	xxx(xx.xx), [xxx]	xxx(xx.xx), [xxx]
...	xxx(xx.xx), [xxx]	xxx(xx.xx), [xxx]
Total	xxx(xx.xx), [xxx]	xxx(xx.xx), [xxx]

[§]Overlapped, MedDRA latest version

E: Number of adverse events

[Table 33] Adverse events and adverse drug reactions of geriatric subjects (aged ≥ 65) (N=xxx)

System Organ Class [§] Preferred Term	Adverse events	Adverse drug reactions
	n(%), [E]	n(%), [E]
System Organ Class	xxx(xx.xx), [xxx]	xxx(xx.xx), [xxx]
Preferred Term	xxx(xx.xx), [xxx]	xxx(xx.xx), [xxx]
...	xxx(xx.xx), [xxx]	xxx(xx.xx), [xxx]
Total	xxx(xx.xx), [xxx]	xxx(xx.xx), [xxx]

[§]Overlapped, MedDRA latest version

E: Number of adverse events

[Table 34] Adverse events and adverse drug reactions in the subjects with renal impairment (N=xxx)

System Organ Class [§] Preferred Term	Adverse events	Adverse drug reactions
	n(%), [E]	n(%), [E]
System Organ Class	xxx(xx.xx), [xxx]	xxx(xx.xx), [xxx]
Preferred Term	xxx(xx.xx), [xxx]	xxx(xx.xx), [xxx]
...	xxx(xx.xx), [xxx]	xxx(xx.xx), [xxx]
Total	xxx(xx.xx), [xxx]	xxx(xx.xx), [xxx]

[§]Overlapped, MedDRA latest version

E: Number of adverse events

[Table 35] Adverse events and adverse drug reactions in the subjects with hepatic impairment (N=xxx)

System Organ Class [§] Preferred Term	Adverse events	Adverse drug reactions
	n(%), [E]	n(%), [E]
System Organ Class	xxx(xx.xx), [xxx]	xxx(xx.xx), [xxx]
Preferred Term	xxx(xx.xx), [xxx]	xxx(xx.xx), [xxx]
...	xxx(xx.xx), [xxx]	xxx(xx.xx), [xxx]
Total	xxx(xx.xx), [xxx]	xxx(xx.xx), [xxx]

[§]Overlapped, MedDRA latest version

E: Number of adverse events

Dummy Table

[Table 36] Reasons for excluding safety evaluation (N=xxx)

Reasons for excluding safety evaluation	No. of subjects n(%)	Incidence of AE n(%)
Reasons for excluding safety evaluation 1)	xxx(xx.xx)	xxx(xx.xx)
Reasons for excluding safety evaluation 2)	xxx(xx.xx)	xxx(xx.xx)
Total	xxx(xx.xx)	xxx(xx.xx)

[Table 37] Adverse events and adverse drug reactions in the subjects excluded from safety analysis
(N=xxx)

System Organ Class [§] Preferred Term	Adverse events	Adverse drug reactions
	n(%), [E]	n(%), [E]
System Organ Class	xxx(xx.xx), [xxx]	xxx(xx.xx), [xxx]
Preferred Term	xxx(xx.xx), [xxx]	xxx(xx.xx), [xxx]
...	xxx(xx.xx), [xxx]	xxx(xx.xx), [xxx]
Total	xxx(xx.xx), [xxx]	xxx(xx.xx), [xxx]

[§]Overlapped, MedDRA latest version

E: Number of adverse events

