### **3.9.2. Interim Analysis**

As required by MFDS regulations, the periodic report should be submitted to MFDS every 6 months for the first two years and then annual report should be submitted to MFDS for the third, fourth and fifth year. The final report for the date collected until August 21, 2018 should be submitted in the sixth year, by November 21, 2018. For the additional study period, periodic report should be submitted to MFDS every 6 months, and the final report of the entire study period should be submitted by November 21, 2021. Interim analysis will be performed in time for the report submission.

Analysis will be performed for safety group and efficacy group for patients who are prescribed with INLYTA® for the first time and for patients who are already on INLYTA® separately, and for all enrolled patients.

- Safety group: Subjects who have been administered INLYTA® at least once and evaluated with safety-related endpoints at least once.
- Efficacy group:ITT (Intent-to-treat) group - subjects to whom INLYTA® is administered INLYTA® at least once.

Detailed methodology for summary and statistical analyses of data collected in this study will be documented in a Statistical Analysis Plan (SAP), which will be dated, filed and maintained by the sponsor. The SAP may modify the plans outlined in the protocol; any major modifications of primary endpoint definitions or their analyses would be reflected in a protocol amendment.

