3.1. Safety Analysis Set

Safety analysis set will be included all subjects who have been administered INLYTA® at least once and evaluated with safety-related endpoints at least once.

The case below shall be excluded from the safety analysis set in the following order:

- 1) Subjects who have been already completed for INLYTA® prior to the contract date.
- 2) Subjects who have not been administered INLYTA®.
- 3) Subjects who have not met the inclusion/exclusion criterion.
- 4) Subjects who have not been evaluated for any safety-related endpoints.
- 5) Subjects who have any significant protocol violation.

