3.5. Population excluded from Safety Analysis

Population excluded from safety analysis will be reported separately with descriptive analysis only (number, percentage of subjects with adverse events and number of adverse events). However, subjects who have not been administered for INLYTA® will be excluded from this analysis set.

4. Study Endpoints

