6.2. Safety Analyses

Safety analyses will be performed based on data of safety analysis set. All adverse events in CRF will be classified by System Organ Class (SOC) and Preferred Term (PT) according to the latest version of Medical Dictionary for Regulatory Activities (MedDRA).

- 1) All adverse events investigated after administration of INLYTA® will be summarized with the number of subjects having adverse events, incidence of adverse events with 95% confidence interval (CI) and the number of adverse events by categorizing as follows.
 - Serious adverse events and serious adverse drug reactions
 - Unexpected serious adverse events and unexpected serious adverse drug reactions
 - Unexpected adverse events and unexpected adverse drug reactions
 - Adverse events and adverse drug reactions
- 2) All adverse events investigated after administration of INLYTA® will be summarized with the frequency and percentage of adverse events by categorizing as follows.

Statistical Analysis Plan for rPMS

- Occurrence status of adverse events by their severity
 - Grade 1 (Mild)
 - Grade 2 (Moderate)
 - Grade 3 (Severe or medically significant)
 - Grade 4 (Life-threatening consequences)
 - Grade 5 (Death related to AE)
- Occurrence status of adverse events by their outcome
 - Recovered
 - Recovered with sequelae
 - Recovering
 - Not recovered
 - Unknown
- Occurrence status of adverse events by their seriousness
 - SAE
 - Results in death
 - Is life-threatening
 - Requires inpatient hospitalization or prolongation of hospitalization
 - Results in persistent or significant disability/incapacity (substantial disruption of the ability to conduct normal life functions)
 - Results in congenital anomaly/birth defect
 - Other important medical event: if it is determined that the event may jeopardize the subject or may require intervention to prevent one of the other outcomes listed in the definition above
 - Non-SAE
- Occurrence status of adverse events by their causality to INLYTA®
 - Related to INLYTA®: ① Certain
 - ② Probable/likely
 - ③ Possible
 - ⑤ Conditional/unclassified
 - ⑥ Unaccessible/unclassifiable
 - ⑦ Not applicable
 - Not related to INLYTA®: ④ Unlikely
- Occurrence status of adverse events by their other causality (In case of 'not related to INLYTA®')
 - Disease under the study
 - Other diseases
 - Concomitant treatment drug or non-drug

Statistical Analysis Plan for rPMS

- Others
- Occurrence status of adverse events by action

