 - Discontinuation (permanently, temporarily or delayed)
 - Dosage reduced
 - Dosage increased
 - No change
 - Unknown
 - Not applicable
- 3) Occurrence status of adverse events by demographic and other baseline characteristics
 - The incidence of adverse events and 95% CI will be presented by categorical variables of demographic and other baseline characteristics.
 - To identify statistically significant difference in incidence of adverse events by categorical variables of demographic and other baseline characteristics, Chi-square test (χ^2 test) or Fisher's exact test (if the expected frequency for each cell under 5 is more than 20%) will be performed.
- 4) Analysis of factors that affect the safety
 - In the re-examination report, logistic regression or multivariate analysis will be performed and an odds ratio with 95% CI and p-value will be presented to identify the factors that affect incidence of adverse events in demographic and other baseline characteristics.
- 5) Analysis for special patient populations [pediatric subjects (aged < 19 years), geriatric subjects (aged \geq 65 years), subjects with renal impairment, subjects with hepatic impairment]
 - Adverse events and adverse drug reactions collected in each special patient population will be presented the number of subjects having adverse events, incidence of adverse events and the number of adverse events for each SOC and PT.
- 6) Analysis for population except from safety analysis
 - Adverse events and adverse drug reactions collected in population except from safety analysis will be presented the number of subjects having adverse events, incidence of adverse events and the number of adverse events for each SOC and PT.

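### Serious and unexpected events in dosed subjects excluded from the safety set are not identified as such in any planned summary

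*SAP*

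**What the plan says.** SAP 6.2 opens by fixing the population: "Safety analyses will be performed based on data of safety analysis set". The outputs of that section include the serious, unexpected serious and unexpected summaries (Tables 8, 9, 11 and 13), the matching subject listings (Tables 10, 12 and 14) and the breakdown by seriousness category (Table 18).

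SAP 3.1 lists five grounds for exclusion from the safety set. Three of them can apply to a subject who was dosed and has safety data:

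- Reason 1: "Subjects who have been already completed for INLYTA® prior to the contract date"
- Reason 3: "Subjects who have not met the inclusion/exclusion criterion"
- Reason 5: "Subjects who have any significant protocol violation"

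For the excluded population, SAP 3.5 says it will be "reported separately with descriptive analysis only (number, percentage of subjects with adverse events and number of adverse events", and it leaves out subjects who never took the drug. SAP 6.2 item 6 repeats the plan: "Adverse events and adverse drug reactions collected in population except from safety analysis will be presented the number of subjects having adverse events", together with incidence and event counts by SOC and PT. The shells follow this. Table 36 gives the number of subjects and any-AE incidence for each exclusion reason. Table 37, titled "Table 37] Adverse events and adverse drug reactions in the subjects excluded from safety analysis", has an AE column and an ADR column.

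Protocol 3.9.2 defines the safety group more simply: "Subjects who have been administered INLYTA® at least once and evaluated with safety-related endpoints at least once".

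**The concern.** The study exists to monitor use of the drug in routine practice, including adverse events. The subjects described in SAP 3.5 were all exposed. Some of them may be the less typical users, because failing an eligibility criterion is one of the ways into this group. If one of them has a fatal or unexpected serious reaction, the study report would show it only as part of a preferred-term count in Table 37. A reader could not tell from that count whether the event was serious, or whether it was expected. The SAE totals would then describe the safety set accurately and still understate what was seen in all dosed enrolled subjects.

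**Working it through.** The plan states no figure on this point, so there is none to reproduce. The check is one of table coverage, followed by an illustration of scale.

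**Who is affected.** Reason 2 in SAP 3.1 covers subjects who were never dosed, and SAP 3.5 drops them from the excluded population. Reason 4 covers subjects with no safety evaluation, who should contribute no events. That leaves reasons 1, 3 and 5.

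**What each output shows.**

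| Output | Population | Seriousness shown | Expectedness shown |
|---|---|---|---|
| Table 8 | Safety set, by sub-group and total | Yes | Yes |
| Tables 9, 18 | Safety set | Yes | No |
| Table 11 | Safety set | Yes | Yes |
| Table 13 | Safety set | No | Yes |
| Listings 10, 12, 14 | Safety set, from the lead sentence of SAP 6.2; rows tagged Sub-group 1 or 2 | Yes | Yes |
| Table 36 | Excluded | No (any AE only) | No |
| Table 37 | Excluded, dosed | No (AE and ADR only) | No |

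The sub-group tag in the listings points the same way. SAP 3.4 defines the two sub-groups for the safety and efficacy sets, and no listing is planned for excluded subjects. SAP 6.2 item 1 speaks of all adverse events after administration. That does not bring excluded subjects in, because the section's first sentence sets the population and item 6 handles them separately.

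**Protocol against SAP.** Protocol 3.9.2 asks for one dose and one safety evaluation. SAP 3.1 starts from the same definition and then adds reasons 1, 3 and 5. A subject can therefore be in the protocol's safety group and outside the SAP's.

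**Scale, on assumed inputs.** Let k be the number of excluded dosed subjects and p the probability that such a subject has an SAE. Neither is in the documents.

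- Expected subjects with an SAE not shown as serious in any summary = k × p
- Probability of at least one = 1 − (1 − p)^k

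For example, with k = 5 and p = 0.1, the expected number is 0.5 and the probability is 1 − 0.9^5 = 0.41.

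| k | Expected, p = 0.1 to 0.4 | P(at least one), p = 0.1 | p = 0.2 | p = 0.3 | p = 0.4 |
|---|---|---|---|---|---|
| 0 | 0 | 0 | 0 | 0 | 0 |
| 2 | 0.2 to 0.8 | 0.19 | 0.36 | 0.51 | 0.64 |
| 5 | 0.5 to 2.0 | 0.41 | 0.67 | 0.83 | 0.92 |
| 10 | 1.0 to 4.0 | 0.65 | 0.89 | 0.97 | 0.99 |
| 20 | 2.0 to 8.0 | 0.88 | 0.99 | 0.999 | about 1.00 |

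For context, the minimum enrolment in protocol 3.6 is 100 eligible subjects. The result depends almost wholly on k. With few exclusions the gap may never arise; with ten or more it is more likely than not at every p shown.

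**The case against.** The other side has a fair case.

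- **The totals are right for the set they describe.** SAP 3.1 defines the set and the tables report it. This stands. A reader might infer that the SAE totals are wrong or certainly incomplete. The documents do not support that, because a shortfall exists only if an excluded dosed subject has an SAE.
- **The plan does not hide these subjects.** Tables 36 and 37 report them by exclusion reason, and by AE and ADR within SOC and PT, with subject and event counts. This also stands. The gap is limited to seriousness, expectedness and the listings.
- **The protocol is not as broad as its safety-group sentence suggests.** Eligibility applies at enrolment (protocol 3.2), and protocol 3.9 lets the SAP modify the plan. Ineligible subjects are therefore enrolment errors and not a planned stratum. Protocol 3.5.4.1 refers to all enrolled patients, which could be read as a promise to include excluded subjects in the SAE tables. In 3.9.2 the phrase sits beside the two treatment-start cohorts within the safety and efficacy groups, so it more naturally means the pooled total.
- **Individual SAEs still reach the sponsor.** Protocol 5.1.1 requires reporting within 24 hours. That protects case handling but does not put the event into the study report.
- **The listings carry no population statement of their own.** True. Their restriction is inferred from the opening of SAP 6.2, which is the natural reading and not an explicit rule.
- **Ascertainment may differ.** Protocol 3.5.4.9.1 describes chart collection for patients on the drug at enrolment, and 5.1.2 starts the reporting period at consent for those already exposed. Neither describes subjects who had finished before the contract date. This is a good reason not to pool them with the safety set.
- **The layout may be prescribed.** Protocol 3.12 says the SAP follows the regulator's post-marketing guideline, which is not available here. That could explain the shells, but nothing in the documents rules out an added column or listing row.

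**Conclusion.** The point holds in a limited form. Dosed subjects excluded under reasons 1, 3 or 5 of SAP 3.1 are reported only as any AE or ADR, in Tables 36 and 37. A serious or unexpected event in one of them would not be identified as such in any planned summary. On the natural reading of SAP 6.2 it would also be missing from Tables 10, 12 and 14. The SAE totals are complete for the safety set and may be incomplete for all dosed enrolled subjects.

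The size cannot be determined from the documents. It is zero if no excluded dosed subject has an SAE. Over the assumed range of 2 to 20 excluded subjects and SAE risks of 10% to 40%, the chance of at least one affected subject runs from 19% to nearly 100%. Those figures show sensitivity to the assumptions and do not predict what will happen. The finding concerns completeness of reporting. It does not show that events go uncollected, or that the safety-set estimates are biased for the population they define.

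**What to change.** Keep the analysis sets as they are.

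1. In SAP 3.5, SAP 6.2 item 6 and Table 37, add n(%), [E] columns for serious AEs and ADRs, unexpected AEs and ADRs, and unexpected serious AEs and ADRs.
2. Extend listing Tables 10, 12 and 14 to excluded dosed subjects, with a column giving the SAP 3.1 exclusion reason.
3. Report these subjects separately and do not pool them into Table 8, because event ascertainment may differ for those who completed treatment before the contract date.

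Tables 32 to 35 need no change for this purpose. They cover special populations within the safety set, whose serious events already appear in Tables 8 to 14.

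Protocol 5.1.1 already requires all SAEs on the CRF, so the change asks for no new data item. Expectedness would have to be assigned to these events as it is for the safety set. The cost is SAP wording, slightly longer tables and possibly more SAEs shown in the report.
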